5.1.5. Dose

Dose will be the current daily dose as described in Table 6.

The current daily dose will be derived from pill strength and dosage recommendations as described in Section 5.1.5.

5.1.6. Definition of continuous treatment and discontinuation

Continuous treatment

Continuous treatment is defined as having consecutive treatment episodes separated by a grace period of 30 days (Figure 1). In a sensitivity analysis, the grace period is extended to 90 days.

In case of overlaps between treatment episodes (i.e., a new prescription/dispensation during an ongoing exposure period), the overlapping days are added to the end of the following treatment episode, resulting in a longer treatment episode to take into account possible stockpiling.

Treatment discontinuation

Treatment discontinuation (see Table 4) is defined either by

- The start of a new prescription of any new drug from the following drug groups: empagliflozin, DPP-4 inhibitors, or SGLT-2 inhibitors), or of a fixed-dose combination of a SGLT-2 inhibitor with a DPP-4 inhibitor (identified from the ATC class A10BD)
- The end date of the first continuous exposure period of the index drug (stop date) plus a 3-month (90 days) period following it.

The discontinuation date is defined as the stop date/start date of a new drug plus 90 days.

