6. RATIONALE AND BACKGROUND

Jardiance (empagliflozin), a highly potent and selective inhibitor of the sodium glucose co-transporter 2 (SGLT-2), was approved in Europe in May 2014 for the treatment of type 2 diabetes (T2D) to improve glycaemic control in adults. Synjardy (empagliflozin/metformin hydrochloride) was approved in Europe in May 2015. SGLT-2 is highly expressed in the kidney; as the predominant glucose transporter, it is responsible for the reabsorption of glucose from the glomerular filtrate back into the circulation. Empagliflozin improves glycaemic control in patients with T2D by reducing renal glucose reabsorption [R14-4617].

The recommended starting dose is 10 mg empagliflozin once daily. In patients tolerating empagliflozin 10 mg once daily who have an estimated glomerular filtration rate (eGFR) \geq 60 mL/min/1.73 m² and need tighter glycaemic control, the dose can be increased to 25 mg once daily. The maximum daily dose is 25 mg [R14-4617].

In Europe, empagliflozin/metformin hydrochloride is available in the following fixed-dose combinations:

- 5 mg empagliflozin plus 850 mg or 1000 mg metformin hydrochloride
- 12.5 mg empagliflozin plus 850 mg or 1000 mg metformin hydrochloride

The recommended dose for the fixed-dose combinations is one tablet twice a day [R17-0153]. Currently, little information is available on whether there is a potential increased risk of cancers of the urinary tract associated with empagliflozin use. Clinical data with empagliflozin has not identified or established a potential mechanism for the development of malignancies. However, “urinary tract malignancies” are listed in the Risk Management Plan (RMP) as a potential risk. The inclusion of renal cancer as a potential risk was based on preclinical toxicology findings and clinical cases of bladder cancer observed with other SGLT-2 inhibitors.

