8.3.1 Exposures

Empagliflozin (current ATC code A10BK03, previous ATC code A10BX12) is the exposure of interest, free or fixed-dose combination with metformin (ATC code: A10BD20).

The DPP-4 inhibitor comparator exposure group will consist of the following drugs, free or fixed-dose combination with metformin (See [Section 8.1](#) and [Annex 4](#)).

- Alogliptin
- Linagliptin
- Saxagliptin
- Sitagliptin
- Vildagliptin

If additional DPP-4 inhibitors are introduced in any of the study countries during the study period, they will also be considered to be members of the corresponding comparator group. Note that use of any of these index drugs prior to index date is an exclusion criterion.

Information on whether patients received prior oral glucose lowering therapy or if they were “added on” or “switched to” empagliflozin, or a DPP-4 inhibitor at the time of inclusion in the study will be collected. Patients will be classified according to their treatment complexity as receiving monotherapy, dual combination therapy, or triple combination therapy and according to use of metformin combination therapy (fixed-dose or free combination). (See Section 8.1)

The primary definition of exposure, i.e., as-treated analysis (AT), is defined as an ongoing exposure (free or fixed-dose combination with drugs other than DPP-4 inhibitors and SGLT-2 inhibitors) to one of the following two index drugs or drug groups: empagliflozin or DPP-4 inhibitors ([Table 3](#), Annex 4). Exposure is defined as use of these drugs during the study period starting from 6 months after the index date (see [Sections 8.2.3](#) and [8.3.5](#))

As a typical prescription length is one month in the UK and three months in Sweden and Finland, multiple prescriptions are required for a patient to have continuous ongoing treatment at 6 months after index date. Therefore, patients with only one prescription are unlikely to contribute to the AT analysis.

Secondary definitions of exposure include cumulative dosage of empagliflozin use, daily dosage of empagliflozin prescribed per use (10mg vs 25mg), and time since first dose of empagliflozin ([Table 3](#), Annex 4).

Sensitivity analyses of exposure include intention-to-treat (ITT) analyses.

Table 3

Exposure definitions for primary and secondary analyses

Exposure definition	Description	Time-dependent or Fixed at index date

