5.1.4. Days' supply and duration of exposure

The estimated days' supply of each prescription/dispensing will be used to determine exposure episodes. Continuous exposure periods will then consist of consecutive exposure episodes separated by a gap of at most 30 days (Section 5.1.6).

The construction of exposure episodes is based on the assumptions that the total prescribed/dispensed dose is consumed as 1 unit per day, 1 defined daily dosage (DDD) per day, or 1 prescribed daily dose (PDD) per day. The construction of exposure episodes using PDD exhibited better performance and led to fewer outcome misclassifications, compared to the alternative approaches [4]. In this study, the length of each exposure episode (days' supply) will be calculated at the prescription level as the total prescribed/dispensed doses divided by the daily dose.

The total doses will be calculated as the total number of product units per prescription, using corresponding variables including the package size, unit strength and prescribed number of packages. The daily dose in product units will be determined based on the PDD (or recommended daily dose) and the unit strength in the prescribed packages. For study drugs, the daily doses will be ascertained from recommended dosages and pill strength. In case of missing information, the days' supply will be estimated as the median days' supply of the same drug prescription. The available variables will be extracted from the relevant databases, as described below.

Proprietary confidential information © 2024 Boehringer Ingelheim International GmbH or one or more of its affiliated companies

UK CPRD-GOLD and Aurum

The total doses will be estimated as the total number of prescribed units using the follow variables provided by CPRD:

- Number of individual product packs prescribed
- Pack size
- Unit strength of the product

For study drugs and metformin, daily dose and days' supply will be derived from pill strength and dosage recommendations. For other drugs, the daily dose will be ascertained based on the prescribed daily dose (if available) or defined daily dose and the unit strength of the dispensed packages.

Sweden

The total doses will be calculated as the total number of dispensed units using the follow variables:

- Size of dispensed package
- Number of dispensed packages
- Drug strength

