5.1.8. SECONDARY EXPOSURE DEFINITIONS

Exposure definitions based on dosage or duration

Table 6 Exposure definitions based on dosage or duration

Exposure	Definition	Details	Data source
Cumulative dose of empagliflozin use in grams	Time-updating cumulative sum of empagliflozin dose consumption based on the daily prescribed dose and purchased amounts since the start of follow-up. ATC codes for empagliflozin in Annex II.	Time-dependent Categorical ¹ : Never 0 - <cumulative dose Q1 ≥ Q1 to < Q2 ≥ Q2 to < Q3 ≥ Q3	UK: CPRD Sweden: SPDR Finland: FPR
Daily dose of empagliflozin	The dosage of empagliflozin prescribed per daily use (10mg vs. 25mg). ATC codes for empagliflozin in Annex II.	Time-dependent Categorical: Never 10 mg 25 mg	UK: CPRD Sweden: SPDR Finland: FPR
Updating from index date onwards.*			

Proprietary confidential information © 2024 Boehringer Ingelheim International GmbH or one or more of its affiliated companies

Cumulative exposure duration to empagliflozin in months	Time-updating cumulative sum of duration since the first use of empagliflozin (alone or in combination with metformin), in months. ATC codes for empagliflozin in Annex II.	Time-dependent Categorical ² : Never 0 - < cumulative duration Q1 Updating from index date onwards.* ≥ Q1 to < Q2 ≥ Q2 to < Q3 ≥ Q3	UK: CPRD Sweden: SPDR Finland: FPR
---	--	--	--

*The last observed value will be carried forward for 3 months (90 days) to account for the 90-day delay between end of treatment and treatment discontinuation as defined in Section 5.1.6.

¹ The categories are defined based on the quartiles of overall cumulative dose (grams) of the study population

² The categories are defined based on the quartiles of overall cumulative exposure duration (months) of the study population

Intention-to-treat exposure definition

The intention to treat exposure definition assumes that individuals do not discontinue the treatment of an index drug.

Table 7 Intention-to-treat exposure definition

Exposure	Definition	Details	Data source
Exposure to index drugs (Intention to treat)	Purchase of empagliflozin (alone or in combination with metformin) or any DPP-4 inhibitors (including combinations). ATC codes for empagliflozin and DPP-4 inhibitors in Annex II.	Time-fixed Categorical: Empagliflozin	UK: CPRD Sweden: SPDR Finland: FPR

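### The stockpiling rule in SAP 5.1.6 has no same-strength condition, so leftover 10 mg supply is coded as 25 mg exposure after a change of strength

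*SAP*

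**What the plan says.** SAP 5.1.4 builds exposure from single prescriptions: the length of each episode "will be calculated at the prescription level as the total prescribed/dispensed doses divided by the daily dose". Each episode therefore has one strength. For dose, SAP 5.1.5 states: "The current daily dose will be derived from pill strength and dosage recommendations as described in Section 5.1.5". That reference points back to its own section.

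SAP 5.1.6 handles overlaps. The trigger is "a new prescription/dispensation during an ongoing exposure period", and then "the overlapping days are added to the end of the following treatment episode, resulting in a longer treatment episode". No condition on strength is attached. The same section allows gaps of 30 days within continuous treatment and sets as-treated censoring at the stop date plus 90 days. A change of strength is not a switch: 5.1.6 and the note to Figure 1 in 5.1.3 require a new drug other than the index drug.

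SAP Table 6 defines a time-dependent daily dose (never, 10 mg, 25 mg) and carries its last value forward for 90 days. It defines cumulative dose as "Time-updating cumulative sum of empagliflozin dose consumption based on the daily prescribed dose and purchased amounts since the start of follow-up".

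Protocol section 6 foresees the change of strength. It says "The recommended starting dose is 10 mg empagliflozin once daily" and allows an increase to 25 mg under stated conditions. Protocol 8.3.4 has no stockpiling rule, so SAP 5.1.6 is the only text on the matter.

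**The concern.** Carrying days forward suits an early refill of the same tablet, where the patient holds more of the same supply. After a change of strength, the leftover days belong to a different dose. Appended to the new episode, they take the new episode's pill strength. Nothing in the SAP keeps the dose of the supply they came from, and nothing closes the earlier episode.

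The comparison of 10 with 25 mg is a stated secondary objective for all three primary outcomes. Protocol 6.4 shows why it is of interest: in the empagliflozin trial, bladder cancer was seen in three patients on 10 mg, nine on 25 mg and five on placebo. A coding rule that moves time between the two dose categories blurs that contrast. The same days also postpone the as-treated stop date and widen the gap that counts as continuous treatment.

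**Working it through.** The documents give no figure to reproduce, so the rule is followed step by step on one patient.

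**Inputs**
- Supply length: "As a typical prescription length is one month in the UK and three months in Sweden and Finland" (Protocol 8.3.1), taken as 30 and 90 days.
- Gap of 30 days and tail of 90 days (SAP 5.1.6).
- Assumed: a 90-tablet 10 mg pack on day 0; four 90-tablet 25 mg packs on days 30, 120, 210 and 300, one tablet daily, with 25 mg taken from day 30. The day of the change is a chosen value.

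**Leftover supply.** L = 90 − 30 = 60 days.

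**Episodes under 5.1.6.** The first 25 mg episode runs from day 30 to 120 + 60 = 180. The refill on day 120 again overlaps by 60 days, which roll forward. The last episode ends on day 390 + 60 = 450.

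| | SAP rule | Same-strength carry-over only |
|---|---|---|
| 25 mg days before the tail | 450 − 30 = 420 | 390 − 30 = 360 |
| Stop date | day 450 | day 390 |
| Censoring (stop + 90) | day 540 | day 480 |
| Censoring after last 25 mg tablet | 150 days | 90 days |

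The 25 mg supply covers 360 days, and 420 are labelled 25 mg (420/360 = 1.17). From day 30 to day 390 the label is right; the surplus lies between day 390 and day 450.

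**Cumulative dose from index date**
- Dose times days: 30 × 10 + 420 × 25 = 10,800 mg = 10.8 g.
- Purchased: 90 × 10 + 360 × 25 = 9,900 mg = 9.9 g.
- Leftovers discarded: 30 × 10 + 360 × 25 = 9,300 mg = 9.3 g.

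Dose times days thus exceeds the purchased amount by 9% (10.8/9.9) and the discarded-leftover total by 16% (10.8/9.3).

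**Gap.** If the patient stops on day 390 and restarts 85 days later, on day 475, the computed gap is 475 − 450 = 25 days. That is within 30, so treatment is called continuous. In general the tolerated gap is 30 + L days.

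**Range of L.** L is zero if the change coincides with a renewal, and at most about one supply length per change. Against the mean follow-up in Protocol 8.5, the upper limits are:
- UK: 30/(2.4 × 365.25) = 3.4%
- Sweden: 90/(2.2 × 365.25) = 11.2%
- Finland: 90/(2.4 × 365.25) = 10.3%

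**Decrease.** With 25 mg on day 0 and 10 mg on day 30, the 60 leftover 25 mg days become 10 mg days.

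**The case against.** The strongest reply is that the error is confined to certain patients and to a certain stretch of time. If the new strength is taken from the day it is supplied, on-treatment time is labelled correctly. The surplus appears only after the last tablet or in a gap. Table 6 already intends a 90-day carry-forward of the dose there, so the worked patient's tail grows from 90 to 150 days. No surplus arises when follow-up ends on treatment through cancer, death, emigration or end of study, or at a switch, which is dated from the new drug. All of this stands, and it limits the size.

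Two further replies also stand. Leftover tablets may be finished later, in which case the later stop date is right and only the dose label is wrong. Cumulative dose names purchased amounts as well as daily dose, and purchased amounts contain no surplus 25 mg tablets. The 10.8 g figure needs a pure dose-times-days formula that the SAP does not state.

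It may also be said that planned sensitivity analyses cover the matter. The 180-day tail and the intention-to-treat analysis do bear on late censoring. But SAP Table 16 lists them for urinary tract cancer only and without the dose exposures. It lists the 90-day grace-period analysis under the intention-to-treat definition, where discontinuation does not censor. None of these analyses removes the carry-over.

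Annex IV is not reproduced in the published text. It is described as a list of drug dosages, so it may not settle overlaps, but this cannot be checked.

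**Conclusion.** The point holds as a coding fault in the secondary dose analyses. After an increase with leftover supply, the L carried days correspond to 10 mg tablets or to no tablets, never to 25 mg supply. The 10 versus 25 mg analysis is therefore misclassified for patients who stop or have a gap after a strength change. Cumulative dose is inflated only on the dose-times-days reading. In the as-treated analysis the stop date moves up to L days later and the tolerated gap rises to 30 + L days. That effect is modest and can also arise from strength changes among DPP-4 inhibitors.

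A reader might infer that such patients are common, that leftover tablets are never taken, that the 30-day rule fails altogether for titrated patients, or that the primary hazard ratio is seriously biased. The documents do not support these. Protocol section 6 makes the increase conditional on tolerance, renal function and need for tighter control. Neither document gives its frequency, the supply then left, or what becomes of it. The 30-day rule is loosened by L days, and not at all when L is zero. The primary exposure is time-fixed and carries no dose label.

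The assumptions are the value of L and the reading that a lengthened episode keeps its own pill strength. The SAP implies that reading but does not state it.

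**What to change.** In SAP 5.1.6, limit carry-over to overlapping prescriptions or dispensings of the same active ingredient(s) and strength, regardless of pack size or article number. The last clause matters in Finland, where records carry an article number: matching at that level would discard genuine stock when only the pack changes. When strength changes within the index drug, end the earlier episode on the day before the new supply, do not carry its remaining days into the new-strength episode, and take the daily dose from the newest supply. Correct the circular reference in 5.1.5, and state in Table 6 how daily dose and purchased amounts combine into cumulative dose.

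The cost is a short text change and one condition in the episode-building code. The downside is that patients who later finish old tablets lose those days, which the 30-day grace period partly covers. Keeping the original dose label on carried days would also correct the label, but it would leave the later stop date and the wider gap in place. The change concerns exposure coding only, not how any patient is dosed.

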5.1.7. Primary Exposure definition

The primary definition of exposure, i.e. as-treated exposure (AT), is defined as a continuous exposure to empagliflozin or to a DPP-4 inhibitor, starting from index date. Continuous exposure and treatment discontinuation are defined in Section 5.1.6.

In the Swedish dataset, drug exposure will be identified from SPDR. In Finland, the FPR will be used. In the UK datasets, drug exposure will be identified from CPRD data. The study drugs will be identified using ATC codes (med codes for CPRD) listed in Annex II.

Proprietary confidential information © 2024 Boehringer Ingelheim International GmbH or one or more of its affiliated companies

Table 5 As-treated exposure definition

Exposure	Definition	Details	Data source
Exposure to index drugs (as treated)	Exposure status for empagliflozin (alone or in combination with metformin) or DPP-4 inhibitor (including combinations) based on purchased amounts and daily defined dose. ATC codes for empagliflozin and DPP-4 inhibitors in Annex II.	Time-fixed Categorical: Empagliflozin DPP-4 inhibitor	UK: CPRD Sweden: SPDR Finland: FPR
Evaluated at index date			

5.1.8. SECONDARY EXPOSURE DEFINITIONS

Exposure definitions based on dosage or duration

Table 6 Exposure definitions based on dosage or duration

Exposure	Definition	Details	Data source
Cumulative dose of empagliflozin use in grams	Time-updating cumulative sum of empagliflozin dose consumption based on the daily prescribed dose and purchased amounts since the start of follow-up. ATC codes for empagliflozin in Annex II.	Time-dependent Categorical ¹ : Never 0 - <cumulative dose Q1 ≥ Q1 to < Q2 ≥ Q2 to < Q3 ≥ Q3	UK: CPRD Sweden: SPDR Finland: FPR
Daily dose of empagliflozin	The dosage of empagliflozin prescribed per daily use (10mg vs. 25mg). ATC codes for empagliflozin in Annex II.	Time-dependent Categorical: Never 10 mg 25 mg	UK: CPRD Sweden: SPDR Finland: FPR
Updating from index date onwards.*			

Proprietary confidential information © 2024 Boehringer Ingelheim International GmbH or one or more of its affiliated companies

Cumulative exposure duration to empagliflozin in months	Time-updating cumulative sum of duration since the first use of empagliflozin (alone or in combination with metformin), in months. ATC codes for empagliflozin in Annex II.	Time-dependent Categorical ² : Never 0 - < cumulative duration Q1 Updating from index date onwards.* ≥ Q1 to < Q2 ≥ Q2 to < Q3 ≥ Q3	UK: CPRD Sweden: SPDR Finland: FPR
---	--	--	--

*The last observed value will be carried forward for 3 months (90 days) to account for the 90-day delay between end of treatment and treatment discontinuation as defined in Section 5.1.6.

¹ The categories are defined based on the quartiles of overall cumulative dose (grams) of the study population

² The categories are defined based on the quartiles of overall cumulative exposure duration (months) of the study population

Intention-to-treat exposure definition

The intention to treat exposure definition assumes that individuals do not discontinue the treatment of an index drug.

Table 7 Intention-to-treat exposure definition

Exposure	Definition	Details	Data source
Exposure to index drugs (Intention to treat)	Purchase of empagliflozin (alone or in combination with metformin) or any DPP-4 inhibitors (including combinations). ATC codes for empagliflozin and DPP-4 inhibitors in Annex II.	Time-fixed Categorical: Empagliflozin	UK: CPRD Sweden: SPDR Finland: FPR

